5.2 CONSENTING PARTICIPANTS

A written and signed consent form will be obtained from the recruited disguised caregivers of children under five. A detailed consent form will be developed and will

be translated into Urdu. It will include statements on voluntary participation with refusal to continue at any point of the study with no penalty to the participants. Any queries of the caregivers regarding the study will be resolved prior to signing the

consent form. Those caregivers who will be able to read will be given the opportunity to do so and sign the form and those who will not be able to read will have the consent form read out to them by the data collector in the presence of a witness and thereafter have their thumb impression on the form. The witness will be any other household member over the age of 18 years. The witness will also be asked to sign the form in such a case. In case a caregiver accepts to be a part of the study but refuses to sign the document, he/she will be requested to have a decision maker of the household to sign the form.

No consent will be taken from the observed LHWs and healthcare providers of BHUs, RHCs, private and public healthcare facilities as we shall be conducting disguised observations. This is because if they are taken consent from, prior to the study, they will become cautious and chances are that the observations will not reflect their actual practice as they will change their practices. And considering there will be no harm generated on the part of the researchers and recruited caregivers therefore the benefit of not taking the consent outweighs the risk of taking consent.

5.2.1 Withdrawal of Study Participants

Caregivers will be free to withdraw from the study at any point in time or he/she can be withdrawn from the study by the investigator in case it is felt that the caregiver is not able to contribute to the observation making effectively. In any case, if a withdrawal occurs, the reason will be mentioned in the case report form. Efforts will however be made to ensure maximum retention of participants by providing them financial incentives (that will also cover the transportation and consultation costs).

6 STUDY ASSESSMENTS

6.1 STUDY ASSESSMENTS

The following assessments will be done while doing one time observations using the observation tool (Annex A):

1. History taking: (Did the healthcare provider inquire about the presenting complaints and the predisposing factors which might have led to the complaints)
 - ✓ Cough (presenting complaint)
 - ✓ Fast breathing (presenting complaint)
 - ✓ Laboured breathing (presenting complaint)
 - ✓ Fever (presenting complaint)
 - ✓ Immunization history (Predisposing factor)
 - ✓ Breastfeeding history (Predisposing factor)
 - ✓ Overcrowding (Predisposing factor)
 - ✓ Parental smoking (Predisposing factor)

- ✓ Air pollution (Predisposing factor)
- ✓ Nutritional history (Predisposing factor)
- ✓ Hygienic practices (Predisposing factor)
- ✓ Family history of HIV (Predisposing factor)

2. Examination:

- ✓ Temperature (For fever)
- ✓ Respiratory rate for 1 minute (For fast breathing)
- ✓ Pallor (for anemia indicating malnutrition)
- ✓ Skin rash (for measles)
- ✓ Lower chest indrawing
- ✓ Auscultation for wheeze and/or crepts

3. Diagnosis:

- ✓ Cough with no fast breathing/chest indrawing: No pneumonia
- ✓ With fast breathing and/or chest indrawing : Pneumonia
- ✓ Pneumonia with any danger signs : Severe Pneumonia

4. Management:

- ✓ No Pneumonia: Symptomatic treatment
- ✓ Pneumonia: Oral amoxicillin 40mg/kg/dose twice daily for three days
- ✓ Severe Pneumonia: For LHWs: First dose of oral antibiotic (amoxicillin) and referral to health facility and for health facilities, parenteral ampicillin 50mg/kg IV 6 hourly for five days along with gentamicin 7.5mg/kg/ IM or IV for five days.

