7 DATA COLLECTION

Data will be collected in the form of observations and then entered upon leaving the facility within one hour of the observation. For the purpose of ensuring accurate data entry, the data collector will use the audio recording and the prescription, the copy of which will be kept with them.

A detailed checklist will be used to assess the adherence of the healthcare providers to standard guidelines. This checklist will include all aspects covered in section 6.1:

- ✓ History taking
- ✓ Examination
- ✓ Diagnosis
- ✓ Treatment/management

These areas encompass the guidelines of essential care for pneumonia. Here essential care refers to the questions providers must ask the caregiver and examinations provider must conduct to accomplish correct diagnosis.

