8.2 PROPOSED ANALYSES

Behavioural coding will be employed to prepare the data for analysis. This means that a predetermined code will be given to each variable against each category of observations (History, examination, diagnosis and treatment). Each variable will be answered as "Y" meaning yes, the task was accomplished and "N" meaning no, the task was not accomplished (section 6.1). Additionally, the responses will be labelled as correct, partially correct and incorrect for history taking and examination. If on history taking, the healthcare provider asks questions on all variables, then the responses will be labelled as correct and if any one variable is missed then the response is indicated as partially correct and in case less than 50% of the variables are asked about, then the responses will be labelled as incorrect. The same labels will be specified for the examination. In case of diagnosis and treatment, the labels will be specified as correct and incorrect only as there is no partially correct diagnosis and treatment regimens. The overall frequencies and percentages of these responses will be calculated and cross tabulated across the provinces.

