***RESULT CRITERIA:**

For history taking:

Correct: Score of 12

Partially correct: Score of <12 but >6

Incorrect: Score of <6

For Examination:

Correct: Score of 6

Partially correct: Score of <6 but >3

Incorrect: Score of <3

For Diagnosis:

Correct: 1

Incorrect: 0

For Management:

Correct: 1

Incorrect: 0

Any other pertinent information:

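### The diagnosis key turns on danger signs, but the documents list none and no scored history or examination item is identified as one, so a provider who never assesses severity can be 'correct' on primary endpoints 1 and 2

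*Combined protocol and SAP*

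**What the plan says.** Section 2.2.1 names four primary endpoints: correct history taking, examination, diagnosis and treatment. Section 6.1 and Annex C carry the same content for each.

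- **History:** 12 items, of which 4 are presenting complaints and 8 are predisposing factors.
- **Examination:** 6 items (temperature, respiratory rate, pallor, skin rash, lower chest indrawing, auscultation).
- **Diagnosis:** three classes. The second is "With fast breathing and/or chest indrawing : Pneumonia" and the third is "Pneumonia with any danger signs : Severe Pneumonia". The management rows follow this split.

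On scoring, section 8.2 says "If on history taking, the healthcare provider asks questions on all variables, then the responses will be labelled as correct", and then "The same labels will be specified for the examination". The result criteria in Annex C agree: for history, "Correct: Score of 12", and for examination a score of 6. Diagnosis and management are each scored 1 or 0.

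Section 7 states what the checklist is for: "Here essential care refers to the questions providers must ask the caregiver and examinations provider must conduct to accomplish correct diagnosis". Section 4.2.1 brings severe cases into scope and sends the reader to section 6.1 for their symptoms.

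**The concern.** The step that decides between two of the three diagnoses, and so between two management rows, has no counterpart in the blocks that record what the provider asked and examined. Endpoints 1 and 2 are meant to show whether history and examination meet the standard. As built, they cannot register that severity was never assessed, and they give no credit to a provider who did assess it.

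The separate history and examination endpoints are useful because they show where a wrong diagnosis came from. For the severe class that information is missing. Section 4.2.1 also relies on section 6.1 for the symptoms of severe pneumonia, and section 6.1 names none beyond the general term.

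**Working it through.** **1. Reproduce the tool's totals.** Counting the rows in section 6.1 and Annex C gives history 4 + 8 = 12 and examination 6, which match the maximum scores printed in Annex C. Together, 12 + 6 = 18.

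**2. Count the items identified as a danger sign.** By label, 0 of 18. The items that come closest to severity do not serve that purpose in the documents:

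| Item | How the documents treat it |
|---|---|
| Lower chest indrawing | The key assigns it to pneumonia, not severe pneumonia |
| Laboured breathing | A presenting complaint; not used in the key |
| Breastfeeding and nutritional history | Predisposing factors; not used in the key |
| Temperature | An examination for fever; not used in the key |

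None of these separates the two classes under the plan's own key.

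**3. Apply the scoring rules to a provider who does all 18 items and never looks for a danger sign.**

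| Child | History | Examination | Diagnosis | Management |
|---|---|---|---|---|
| No danger sign | 12/12, correct | 6/6, correct | can be 1 | can be 1 |
| Danger sign present | 12/12, correct | 6/6, correct | normally 0 | normally 0 |

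The first two columns do not change with the child's severity.

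**4. Compare a second provider,** who checks for danger signs and does every listed item except asking about family history of HIV. The history score is 12 − 1 = 11, which is below 12 and above 6, so the label is 'partially correct'. The history endpoint ranks this provider below the one in step 3, although the omitted item plays no part in the diagnosis key.

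**5. Look for another place where severity could be captured.** Neither Annex C nor the eCRF list in section 7.2 has a field for the child's own danger signs or for a reference classification. The documents therefore do not show how the data collector would establish that a severe case was missed.

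**6. Effect of adding rows.** Suppose k danger-sign rows are added to a block (k from 1 to 5 is an assumption, because the documents give no list). The provider in step 3 would then score:

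- History, 12/(12 + k): from 12/13 = 92.3% to 12/17 = 70.6%.
- Examination, 6/(6 + k): from 6/7 = 85.7% to 6/11 = 54.5%.

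All of these lie below the maximum and above 50%. With cut-offs moved to match, the label changes from 'correct' to 'partially correct'.

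**The case against.** **The diagnosis endpoint catches the important failure.** This largely stands. A reader might infer that a provider who ignores severity is certified as correct throughout. The documents do not support that: there are four separate endpoints and no composite, and a missed severe case would normally lose the diagnosis and management points. All four labels are 'correct' without a severity check when the child has no danger sign, or when the provider guesses right.

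**A perfect score is demanding.** Also fair. The wrong label arises only for a provider who completes all 12 or all 6 listed items. The documents do not say how many will, so the effect on reported percentages may be small. The missing credit for checking severity applies at every score.

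**The count of 0 of 18 is a count of labels.** Correct. Because danger signs are never defined, it cannot be settled from the documents whether an item such as laboured breathing or breastfeeding history overlaps with one. What can be said is that the key uses none of them to separate the two classes.

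**Section 7 describes four areas together, and severity appears in the third.** This softens the conflict but does not remove it. Section 7 speaks of questions and examinations, which are the first two areas.

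**There are safeguards.** Visits are audio-recorded, collectors are doctors or nurses trained on the WHO guidelines, the tool is still to be pretested, the examination heading in Annex C allows for other examinations, and there is a free-text line. A recording may recover a question but not a silent inspection. The examination wording and the free-text line are unscored. Nothing in the plan directs the pretest to this gap.

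**A count of affected children.** A reader might apply the background figure in section 1.1 (14 of 120 million episodes becoming severe) to the 160 observations. That is not supported. It is a global count of progression, not the severe share among children found in these communities. Section 4.1 also lets one caregiver serve the LHW, BHU and RHC visits where cases are few, so observations are not children.

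**Conclusion.** The point holds for primary endpoints 1 and 2. Under the stated rules, history and examination can both be labelled 'correct' when severity was never assessed, contrary to the purpose given in section 7. For endpoints 3 and 4 it is limited: a child without danger signs can hide the omission, while a severe child would normally expose a miss without showing whether the assessment was omitted or misjudged.

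Its size is structural: 0 of 18 scored items are identified as a danger sign, and the same form is used at all planned observations, (6 + 4 + 4 + 9 + 9) × 5 = 32 × 5 = 160. How many of these would carry a wrong label cannot be derived, because the severe share and the proportion reaching 12/12 or 6/6 are not given. The conclusion assumes that the item lists in section 6.1 and Annex C are those to be used. It does not depend on any severity rate. In a descriptive study this is a measurement gap that should be fixed before data collection; it does not invalidate the design.

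**What to change.** Before the tablet form is built, and at the latest at the planned pretest:

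1. List in section 6.1 and Annex C the danger signs of the WHO guideline on which the tool already rests, so that the key and the item lists are reconciled. The choice of signs belongs to that guideline and the advisory committee; none is proposed here.
2. Add Y/N rows for them, under History for signs the caregiver reports and under Examination for signs the provider observes, and revise the totals of 12 and 6 and the label cut-offs. Alternatively, keep the present totals and report on its own one row per block recording whether danger signs were asked about or checked. Such a row can be scored consistently only against the list in step 1, and it leaves the endpoint labels themselves unchanged.
3. Add one field for the child's own danger signs, so that the diagnosis can be scored against something recorded.

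The cost is a few more rows, revised totals and cut-offs if rows are added to the score, and slightly longer training, with no extra staff, visits or children. The downside is that, with rows added to the score, 'correct' becomes slightly harder to reach.

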The FLCF level will include observations made at the primary health care facilities which are the Basic Health Units (BHUs) and Rural Health Centres (RHCs). A basic health unit is located within a union council which is the smallest administrative unit in the Pakistani administrative system. Each basic health unit covers a catchment area of 25,000 households. Pakistan has around 5,290 BHUs although not all are functional. Services provided at BHU are promotive, preventive, curative and referral .LHWs refer patients usually to BHUs. RHCs provide in-patient service as compared to BHUs. They usually have 10-20 beds and cover a catchment area of 100,000 people. The RHC provides promotive, preventive, curative, diagnostics and referral services apart from the in-patient services. It also provides clinical, logistical and managerial support to the BHUs, LHWs, and dispensaries that fall within its geographical limits. RHC also provides medico-legal, basic surgical, dental and ambulance services. There are around 552 RHCs in Pakistan.

The practitioner level observations will include those of practitioners at both the private and public sector. The public sector will include observations made in outpatient departments of selected tertiary care hospitals across the study sites. Observations made at the private practitioner level will include selected solitary private clinics or clinics within private hospitals. The community and FLCF level will represent practices within the rural community and the practitioner level will represent practices within the semi urban/urban communities.

3.3 Type of Observations:

These will be participant, structured, disguised observations which will be done using a validated observation tool based on standard WHO pneumonia case management guidelines, developed in close collaboration with experts from University of Edinburgh. This tool will be pretested and translated into Urdu.

3.4 Data Collectors:

A team of data collectors, who will be healthcare professionals, will be trained on appropriate administration of the observation tool upon recruitment. The training will also include an introduction to pneumonia, its signs and symptoms, diagnosis and management according to WHO guidelines. A 3 day interactive training workshop will be conducted whereby mock excesses will also be conducted. A total of three trainings will be conducted whereby data collectors from Islamabad (capital), Punjab

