4.2 INCLUSION CRITERIA

4.2.1 INCLUSION CRITERIA OF DISGUISED CAREGIVERS:

- Caregivers of children under five years of age. These are those individuals who provide direct care to the child. These could either be a mother, father, grandmother or guardian.
- The child under five under that caregiver's household must have symptoms of pneumonia/severe pneumonia as indicated in section 6.1
- Caregivers consenting to be a part of the study.

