7.2 Case Report Forms

Electronic CRFs (eCRFs) will be used for improved data quality, avoidance of manual data entry errors and confidentiality etc. It will include the following key points:

- ✓ Protocol ID
- ✓ Site code
- ✓ Subject ID

- ✓ Respondent Initials
- ✓ Respondent demographics (age, gender, educational level)
- ✓ Age of the youngest child
- ✓ Phone number
- ✓ Alternate phone number
- ✓ Prescription picture
- ✓ GPS location
- ✓ Date of visit
- ✓ Place of visit (LHW/BHU/RHC/Private clinic/Public tertiary hospital)
- ✓ Name of the healthcare provider
- ✓ Data collector initials/ID
- ✓ Time spent in consultation
- ✓ Visit checklist (as indicated by section 6.1)
- ✓ Reason of withdrawal from the study

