ANNEX C- OBSERVATION TOOL

CLINICAL OBSERVATIONS (were the following parameters followed)	
1. History taking	Y/N
Cough	
Fast breathing	
Laboured breathing	
Fever	
Immunization	
Breastfeeding history	
Overcrowding	
Parental smoking/Household member smoking	
Air pollution (indoor cooking stove)	
Nutritional history	
Hygienic practices	
Family history of HIV	
2. Examination (Did the healthcare provider make the following necessary examinations apart from others)	
Temperature	
Respiratory rate counting for 1 minute	
Pallor	
Skin rash	
Examine lower chest in drawing	
Auscultate for wheeze or crepts	
3. Diagnosis (Did the healthcare provider make the correct diagnosis based on WHO guidelines)	
Cough with no fast breathing/chest in drawing: No pneumonia	
With fast breathing and/or chest in drawing : Pneumonia	
Pneumonia with any danger signs : Severe Pneumonia	
4. Management (Did the healthcare provider manage the case per the guidelines)	

No Pneumonia: Symptomatic treatment	
Pneumonia: Oral amoxicillin 40mg/kg/dose twice daily for three days	
Severe Pneumonia: For LHWs: First dose of oral antibiotic (amoxicillin) and referral to health facility and For BHUs: First dose of oral antibiotic (amoxicillin) and referral to rural health centre or tertiary care hospital For health facilities (public and private) : Parenteral ampicillin 50mg/kg IV 6 hourly for five days along with gentamicin 7.5mg/kg/ IM or IV for five days.	

SCORE: (Count the total number of Y and enter the value in the table below)

ACTIVITY OBSERVED	“ Y” SCORED	TOTAL
History Taking		12
Examination		6
Diagnosis		1
Management		1

OBSERVATION RESULT*:

ACTIVITY OBSERVED	SELECT THE APPROPRIATE RESPONSE
History Taking	Correct/partially correct/ incorrect
Examination	Correct/partially correct/ incorrect
Diagnosis	Correct/ Incorrect
Management	Correct/ Incorrect

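### Section 6.1 and Annex C give different severe-pneumonia keys for Basic Health Units, so the same visit can score correct under one text and incorrect under the other

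*Combined protocol and SAP*

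**What the plan says.** Section 6.1, item 4, gives two management rules for severe pneumonia. Lady Health Workers (LHWs) should give a first dose of oral amoxicillin and refer. The rest of the rule reads: "and for health facilities, parenteral ampicillin 50mg/kg IV 6 hourly for five days along with gentamicin 7.5mg/kg/ IM or IV for five days". BHUs are not mentioned separately.

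Annex C, item 4, gives three rules. The LHW rule and the parenteral rule are the same as in section 6.1, but between them stands a rule for BHUs: "First dose of oral antibiotic (amoxicillin) and referral to rural health centre or tertiary care hospital".

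Section 3.2 describes the first level of care as "primary health care facilities which are the Basic Health Units (BHUs) and Rural Health Centres (RHCs". It also says that "RHCs provide in-patient service as compared to BHUs".

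The references to the scoring text point in different directions:

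- Section 6.1 says the assessments are made "using the observation tool (Annex A", but the tool is headed Annex C.
- Section 7.2 defines the eCRF item as "Visit checklist (as indicated by section 6.1".
- Section 8.2 defines the N code as "meaning no, the task was not accomplished (section 6.1".
- The score table and the result criteria appear only in Annex C.

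Severe cases are in scope. Under section 4.2.1 the child "must have symptoms of pneumonia/severe pneumonia as indicated in section 6.1".

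**The concern.** Section 2.2.1 lists correct treatment as a primary endpoint, and section 8.2 allows no partial credit for it. The answer key therefore decides the result completely. If section 6.1 is applied, a BHU that gives the first oral dose and refers the child, as Annex C requires, is recorded as having failed.

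The primary objective looks at practice by level of care. Under section 4.1, where cases are few, the same caregiver may be taken to the LHW, the BHU and the Rural Health Centre (RHC) of one locality. The BHU key then affects how those levels compare on the same child. Section 3.4 also plans three separate training sessions, so an unsettled key could be taught differently in different regions.

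**Working it through.** **1. Planned counts (section 8.1).** Per location: LHW 6, BHU 4, RHC 4, private 9, public 9.

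- Per location: 6 + 4 + 4 + 9 + 9 = 32
- Total over five locations: 32 × 5 = 160, which reproduces the plan's minimum
- BHU: 4 × 5 = 20, and 20/160 = 12.5%
- First-level care facilities (BHU + RHC): (4 + 4) × 5 = 40

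**2. A severe case seen at a BHU, scored under each text.**

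| Management given | Section 6.1 | Annex C |
|---|---|---|
| First oral amoxicillin dose plus referral | 0 | 1 |
| Five days of parenteral ampicillin plus gentamicin | 1 | 0 |
| Neither | 0 | 0 |

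Both listed regimens change score with the text used. Non-severe visits, and the LHW, RHC and practitioner keys, agree between the texts.

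**3. Effect of one rescored visit on percent correct.** This needs no assumption.

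- BHUs in one location: 1/4 = 25 points
- All providers in one location: 1/32 = 3.1 points
- All BHUs: 1/20 = 5 points
- First-level care facilities: 1/40 = 2.5 points
- Overall: 1/160 = 0.6 points

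**4. Upper bounds.** The documents give no severe share among recruited children, so the share *s* is assumed. The bound is *s* for BHUs, 20*s*/40 for first-level facilities and 20*s*/160 overall. It is reached only if every severe BHU visit received the same listed regimen.

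| Assumed *s* | Severe BHU visits | BHU | First-level | Overall |
|---|---|---|---|---|
| 10% | 2 | 10 points | 5 points | 1.25 points |
| 25% | 5 | 25 points | 12.5 points | 3.1 points |
| 50% | 10 | 50 points | 25 points | 6.25 points |

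**5. Net shift.** Let *a* be the share of severe BHU visits given the Annex C regimen and *p* the share given the section 6.1 regimen. The BHU rate under Annex C minus the rate under section 6.1 is *s*(*a* − *p*). With assumed values *s* = 25%, *a* = 40% and *p* = 10%:

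- BHU: 0.25 × (0.40 − 0.10) = 7.5 points
- Overall: 7.5 × 20/160 = 0.9 points

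If *a* = *p*, the net shift is zero, although individual visits are still scored differently.

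**The case against.** **Section 6.1 may be only a summary.** It sends the reader to the observation tool, the tool holds the only score table, and collectors are trained on the tool. The references to section 6.1 in sections 7, 7.2 and 8.2 could be read as naming the four domains and not as setting the key. This supports Annex C as the intended rule, as do its greater detail and the contrast in section 3.2 between RHCs and BHUs on in-patient care. But no text states it, and the eCRF and coding sections cite the other text.

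**Section 6.1 may not mean BHUs at all.** Annex C lists its facilities rule after, and apart from, the BHU rule, so section 6.1 might simply be silent. Section 3.2 counts against this: it classes BHUs as facilities and says LHWs usually refer to them, while the LHW rule in section 6.1 sends the child to a health facility. Even if the reading is right, the text cited for coding then has no severe key for a cadre that must be scored.

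**The size is mostly assumption.** That is so for steps 4 and 5. The plan also does not say it will tabulate BHUs within one location. For the outputs named in section 8.2, one visit moves 0.6 points overall or 3.1 points for a location. The parenteral regimen is probably rare at a BHU, so the likely error runs mainly one way, against BHUs that refer.

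**The error can be caught or repaired.** The tool is to be pretested with advisory committee input. The audio recording, prescription and place of visit are kept, so affected visits could be rescored. That stands, but only if someone notices the mismatch.

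**Conclusion.** The concern holds. Two current texts give different answer keys for the same primary-endpoint item, and neither is said to prevail. At most 20 of the 160 minimum observations are exposed, and of these only severe visits in which a listed regimen was given. The effect per rescored visit is firm: 5 points for all BHUs, 3.1 for a location's total and 0.6 overall. The total effect cannot be fixed from the documents, because the severe share and the regimen rates are not given; the larger figures above are bounds under assumed values. Annex C is very likely the intended rule. Because the item is a primary endpoint scored 0 or 1 and the repair costs almost nothing, it should be corrected before data collection.

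**What to change.** Add the Annex C rule for BHUs to section 6.1, item 4. Alternatively, state in sections 6.1, 7.2 and 8.2 that Annex C governs scoring. In either case, have the advisory committee confirm the rule. Build the eCRF checklist from that single key before collectors are trained.

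Two small corrections can be made at the same time:

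- Point the tool reference in section 6.1 to Annex C.
- Check the gentamicin dosing interval. Both texts, as read, end the dose with a slash and no interval, which may be a loss in text extraction.

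The cost is one line and one cross-reference. Sample size, sites and data burden do not change.
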